8.3 Analysis Populations

The analysis populations include the following:

- The safety population will include all subjects who receive at least one dose of IP. The safety population is the population used for all safety analyses.
- Full Analysis Set (FAS) - All randomized subjects who receive at least one dose of investigational product and have at least one post dose efficacy assessment. The FAS population will be the primary population for the efficacy analyses.
- The Per Protocol (PP) population will include subjects in the FAS population who complete the study without any major protocol violations. The composition of the PP population will be determined and documented in blind reviews of the database conducted prior to unblinding the study database.

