8.7.3 Handling of Missing Values/Censoring/Discontinuations

The primary population for all efficacy analyses will be the FAS population.

For the analyses of the primary endpoints (PASI-75 and IGA) based on the FAS population, several methods will be used to impute missing data, including, multiple imputation (MI), modified non-responder imputation (mNRI), and last-observation-carried forward (LOCF). MI will be the primary imputation method. Sensitivity analyses using LOCF and m-NRI will be performed to assess the robustness of alternate imputation assumptions. In particular, subjects

who used rescue medications or who discontinued due to unsatisfactory therapeutic effect will be included in PP population. These subjects will be considered as treatment failures (i.e., non-responder for both PASI-75 and IGA) for all time points after the initiation of rescue medications or subject discontinuation.

MI: Missing data will be imputed using multiple imputations. MI will be implemented for all subjects with missing data, including those who used rescue medications and those who discontinued due to unsatisfactory therapeutic effect.

MI for missing PASI scores : Intermittent missing values of PASI scores will be imputed separately for each treatment group using the Markov Chain Monte Carlo (MCMC) method, generating 50 copies of the imputed dataset with monotonic missing pattern. For each of the 50 datasets, missing values at scheduled visits (Weeks 4, 8, 12, 16, 20 and 24) will be imputed using a linear regression model. The imputations will include the following variables: baseline BMI, baseline PASI score, and PASI scores at the previous scheduled visits. SAS Proc MI will be used. Imputed PASI-75 response (Yes/No) will be derived for each imputed dataset.

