## 8. ANALYSIS POPULATIONS

The following analysis sets/populations will be used in this trial:

- Safety population: include all subjects who receive at least one dose of IP. The safety population is the population used for all safety analyses.
- Full analysis set (FAS) – All randomized subjects who receive at least one dose of investigational product and have at least one post dose efficacy assessment. The FAS population will be the primary population for the efficacy analyses
- Per Protocol (PP) population: include subjects in the FAS population who complete the study without any major protocol violations that are considered likely to affect the efficacy analysis outcomes of the study. Major protocol violations will include but not be restricted to the following:
  - Failure to meet the inclusion/exclusion criteria that are considered likely to affect the efficacy analysis outcomes of the study
  - Randomization error

- Usage of any prohibited concomitant medications or procedures
- Failure to have Week 24 assessment within the allowable window for either of the co-primary endpoints
- Failure to be compliant with treatment regimen

Additional criteria may be added to determine PP population. The composition of the PP population will be determined and documented in blind reviews of the database conducted prior to unblinding the study database. Subjects who used rescue medications or who discontinued due to unsatisfactory therapeutic effect will be included in the PP population. These subjects will be considered as treatment failures (i.e., non-responder for both PASI-75 and IGA) for all time points after the initiation of rescue medications or subject discontinuation.

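### SAP 8 puts lack-of-efficacy dropouts in the per-protocol population as non-responders, but its completion, Week 24 and compliance criteria exclude them, with no exception stated

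*SAP*

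**What the plan says.** SAP 8 defines PP to "include subjects in the FAS population who complete the study without any major protocol violations" likely to affect the efficacy outcomes. Its list of major violations includes:

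- "Failure to have Week 24 assessment within the allowable window for either of the co-primary endpoints"
- "Usage of any prohibited concomitant medications or procedures"
- "Failure to be compliant with treatment regimen"

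The section closes with the statement that "Subjects who used rescue medications or who discontinued due to unsatisfactory therapeutic effect will be included in the PP population", and scores these subjects as non-responders on both co-primary endpoints from that point on.

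The protocol has the same pair of rules. Section 8.3 limits PP to subjects "who complete the study without any major protocol violations". Section 8.7.3 says that subjects "who used rescue medications or who discontinued due to unsatisfactory therapeutic effect will be included in PP population". Protocol 8.10 adds that major deviations lead to exclusion from PP, and that the SAP prevails where the two documents differ.

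SAP 12.8.1 plans a supporting analysis of both co-primaries on PP with m-NRI. The SAP 9 summary table names m-NRI as the only PP method for the responder endpoints.

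**The concern.** A subject who stops early for lack of efficacy is ruled out of PP by the definition and ruled in by the closing sentence. Neither sentence says that it overrides the other. The protocol cannot settle the matter because it has the same gap, and the SAP-prevails clause does not help because the conflict lies inside SAP 8.

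PP membership for these subjects is therefore not fixed by the text. If the exclusions win, no lack-of-efficacy dropout is left in PP for m-NRI to score as a failure. If the inclusion sentence wins, these subjects enter the denominators as non-responders. Two programmers working in good faith, one from the table shells and one from the closing sentence, would build different PP populations for the supporting analysis of both co-primaries.

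**Working it through.** **1. Completion.** A subject who discontinued for lack of efficacy has not completed the study. This criterion catches every such dropout, whatever the date.

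**2. Compliance (SAP 12.4; Table 14.1.3.1).** The plan's denominator reproduces: titration 28 × 4 + 35 = 147, treatment 42 × 19 = 798, total 945 tablets. It is fixed for the whole study and not cut off at discontinuation. Compliance means 80% to 120%, and the overall figure is the main determinant.

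- Tablets needed: 0.80 × 945 = 756.
- With perfect dosing: 147 by Day 35, then 42/7 = 6 per day.
- Day reached: 35 + (756 − 147)/6 = 35 + 101.5 = 136.5.

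Even a perfectly dosed subject who stops before about Day 137 fails overall compliance. A later stop can pass.

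**3. Week 24 assessment (SAP 11.4).** The Week 24 window opens at Day 155, and only values obtained within 15 days of last dose count as on-treatment. The earliest qualifying last dose is therefore 155 − 15 = Day 140. A known last dose before that cannot give an on-treatment Week 24 value. This takes the allowable window to be the one in SAP 11.4. With the ±3-day visit window in Protocol Table 1-1, the earliest visit is Day 165 and the limit moves to 165 − 15 = Day 150.

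**4. Combined, for a lack-of-efficacy dropout under SAP 11.4**

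| Last dose | Completion | Week 24 value | Overall compliance |
|---|---|---|---|
| Before about Day 137 | fails | fails | fails |
| About Day 137 to Day 139 | fails | fails | can pass |
| Day 140 or later | fails | can pass | can pass |

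**5. Table shells.** Table 14.1.1 lists five reasons for exclusion from PP. Three of them are prohibited medication, no in-window Week 24 assessment and noncompliance, none with an exemption. The footnotes to the PP m-NRI tables (14.2.1.1.2 and 14.2.1.2.2) count in N only subjects who have a Week 24 assessment. That drops the early dropouts whom the inclusion sentence keeps.

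**6. Rescue users.** Protocol 6.7 allows rescue at the investigator's discretion and names no agents. The same section prohibits many active psoriasis therapies and limits permitted psoriasis concomitants to non-medicated measures, apart from mild topical steroids on limited areas and medicated shampoos. A rescue user therefore meets the prohibited-medication criterion only if the agent used is on that list.

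**7. Size (illustration).** Taken from SAP 7: about 50 completers per arm, with response rates of 15% and 45%, so 7.5 and 22.5 responders. Assumed: every completer qualifies for PP, and the dropout splits are as shown, because the documents give none. Rate = responders/(50 + dropouts kept). Odds ratios are unadjusted.

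| Dropouts kept, placebo/active | Placebo | Active | Difference (points) | Odds ratio |
|---|---|---|---|---|
| none | 7.5/50 = 15.0% | 22.5/50 = 45.0% | 30.0 | 4.64 |
| 10/5 | 7.5/60 = 12.5% | 22.5/55 = 40.9% | 28.4 | 4.85 |
| 20/5 | 7.5/70 = 10.7% | 22.5/55 = 40.9% | 30.2 | 5.77 |
| 25/25 | 7.5/75 = 10.0% | 22.5/75 = 30.0% | 20.0 | 3.86 |
| 30/10 | 7.5/80 = 9.4% | 22.5/60 = 37.5% | 28.1 | 5.80 |

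These are not bounds. A more uneven 25/5 split gives 10.0% against 40.9% and an odds ratio of 6.23.

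**The case against.** The best defence is that the closing sentence is a later, specific and mandatory rule that overrides a general list. Planning m-NRI on PP supports this, since m-NRI acts only on lack-of-efficacy dropouts and rescue users. Failure to complete is also not among the five reasons in Table 14.1.1. The override is probably what was meant. It is not written, however, and the fixed 945-tablet denominator, the other Table 14.1.1 reasons and the N footnotes all work against it.

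SAP 8 also requires PP composition to be settled and documented in blinded review. That guards against a choice driven by results, and this part of the defence stands. It does not tell the review which rule to apply.

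Four stronger readings might be inferred, and the documents do not support them:

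- *Every lack-of-efficacy dropout fails three criteria at once.* This holds only for stops before about Day 137. From Day 140 a dropout can fail completion alone.
- *Rescue users are in the same contradiction.* Protocol 6.7 does not say that permitted rescue is a prohibited-medication violation.
- *Under the exclusion reading, PP m-NRI has nothing to impute.* A compliant rescue user with a Week 24 visit can remain in PP, and SAP 9 scores that subject a non-responder whether assessed or not.
- *The treatment effect would be much smaller.* Arm rates fall, but the contrast can move either way. In the 30/10 split the difference goes only from 30.0 to 28.1 points, while the odds ratio rises from 4.64 to 5.80.

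**Conclusion.** The conflict is real for subjects who discontinue for lack of efficacy: taken literally, SAP 8 both includes and excludes them, and the shells follow the exclusion. For rescue users it is conditional on the agent used, and Protocol 6.7 and SAP 8 must be reconciled on that.

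The impact is limited to the supporting PP analysis. The primary analysis is FAS with multiple imputation, and the FAS m-NRI sensitivity analysis is planned separately; neither depends on PP membership. The size cannot be fixed from the documents, because it turns on the number of lack-of-efficacy dropouts in each arm. The tabulated splits give odds ratios of about 3.9 to 5.8, against 4.6 with these dropouts excluded. The day limits rest on perfect dosing, a known last-dose date and the SAP 11.4 window.

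**What to change.** 1. Add one sentence to SAP 8, for example: *The completion, Week 24-window and overall-compliance criteria do not exclude subjects who discontinued for unsatisfactory therapeutic effect or used rescue medication, and permitted rescue use is not by itself a prohibited-medication exclusion from PP.* This concerns population membership only. Which agents may be used as rescue is for Protocol 6.7 and is not altered here.
2. Align the exclusion reasons in Table 14.1.1 with that sentence.
3. In the m-NRI versions of the co-primary tables, redefine N as subjects with a Week 24 assessment or an m-NRI-imputed non-response. Without this, early dropouts leave the denominator even after step 1. The shell is reused for LOCF and OC, so the new wording belongs only in the m-NRI versions.
4. Leave the general compliance rule in SAP 12.4 unchanged. The exception makes a change to the 945-tablet denominator unnecessary.

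The cost is a short SAP wording change and edits to the shells, made before the blinded PP review. SAP 9 already defines how lack-of-efficacy discontinuations are identified on the eCRF, so no new data are needed.

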## 9. HANDLING OF MISSING DATA

All imputations specified in this section will be performed for the Double-Blind Treatment and titration Period only; the Post-treatment Follow-Up Period data will be analyzed as observed.

For the analyses of the co-primary endpoints (PASI-75 and IGA), multiple imputation (MI) will be the primary imputation method. The modified non-responder imputation (m-NRI) and last observation carried (LOCF) method will be used as sensitivity analyses.

Details of the imputation methods are as following:

- **MI:** Missing data will be imputed using multiple imputations, a simulation-based approach where missing values are replaced by multiple Bayesian draws from the conditional distribution of missing data given the observed data and covariates, creating multiple completed data sets. These completed datasets can then be analyzed using standard analysis methods. MI will be implemented for all subjects with missing data, included those who used rescue medications or discontinued due to unsatisfactory therapeutic effect.

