- Topical corticosteroids (other than the limited use of mild topical steroids specified below under "Rescue Medication"), vitamin D analogs, tar preparations, salicylic acid, or urea preparations
- Topical or systemic calcineurin inhibitors (eg, tacrolimus, pimecrolimus)
- Topical or systemic retinoids (eg, tazarotene, tretinoin, adapalene)
- Topical (ointment and/or baths) or oral fumaric acid derivatives
- Cytostatic drugs (eg, cyclophosphamide, ifosfamide, vinblastine, vincristine, procarbazine, dacarbazine, 6-mercaptopurine, 5-fluorouracil, adriamycin)
- Any investigational drug or therapy, or approved drug or therapy for investigational use

Rescue and Concomitant Medication

The use of rescue medications for the treatment of psoriasis may be permitted during the Double-Blind Titration and/or Treatment Period at the investigator's discretion. Subjects will be considered a treatment failure if rescue therapy is required; however, they can continue for safety monitoring, if required. Concomitant medications permitted for use for psoriasis are restricted to bland emollients and other non-medicated interventions. This excludes any topical agents that contain pharmacologically active ingredients (eg, salicylic acid, alpha-hydroxy acids, urea, etc.). Dose adjustments of any permitted concomitant medications should be avoided during the study, if possible.

Note: Limited use of mild topical steroids (Class VI or VII in North America) for the treatment of psoriasis on limited areas (face, axilla, and/or genitalia) is permitted. Subjects will be permitted to use medicated shampoos (on the scalp only in the shower). This will not be considered as rescue medication.

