### Multiple Imputation procedures for missing PASI scores:

Intermittent missing values of PASI scores will be imputed separately for each treatment group using the Markov Chain Monte Carlo (MCMC) method, generating 50 copies of the imputed dataset with monotonic missing pattern. For each of the 50 datasets, missing values at scheduled visits (Weeks 4, 8, 12, 16, 20 and 24) will be imputed using a linear regression model. The imputations will include the following variables: baseline BMI, baseline PASI score, and PASI scores at the previous scheduled visits. SAS Proc MI will be used. Imputed PASI-75 response (Yes/No) will be derived for each imputed dataset.

Example SAS code is as follows:

```
PROC MI DATA = PASI1 OUT = PASI2 SEED = 132138 NIMPUTE = 50 NOPRINT;  
BY TRT01PN;
```

```
MCMC IMPUTE = MONOTONE;  
VAR BASEBMI BASEPASI _3 _4 _5 _6 _7 _8;  
RUN;  
  
PROC MI DATA = PASI2 OUT= PASI3 SEED = 132138 NIMPUTE = 1 NOPRINT;  
BY TRT01PN _IMPUTATION_;  
MONOTONE REGRESSION;  
VAR BASEBMI BASEPASI _3 _4 _5 _6 _7 _8;  
RUN;
```

Multiple Imputation procedures for missing IGA scores:

The imputation of post-baseline IGA scores will be performed following a similar approach as described for PASI scores. Intermittent missing IGA scores will be imputed separately for each treatment group using the Markov Chain Monte Carlo (MCMC) method where 50 copies of the dataset with monotonic missing pattern will be generated. For each of the 50 datasets, missing values at scheduled visits (Weeks 4, 8, 12, 16, 20 and 24) will be imputed using a logistic regression model including baseline BMI, baseline IGA score, and IGA scores at the previous scheduled visits. SAS Proc MI using the logistic regression method for monotone data will be used for the imputation. IGA Treatment Success status (Yes/No) will then be derived for each imputed dataset.

Example SAS code is as follows:

```
PROC MI DATA = IGA1 OUT = IGA2 SEED = 132138 NIMPUTE = 50 NOPRINT;  
BY TRT01PN;  
MCMC IMPUTE = MONOTONE;  
VAR BASEBMI _3 _4 _5 _6 _7 _8;  
RUN;  
  
PROC MI DATA = IGA2 OUT= IGA3 SEED = 132138 NIMPUTE = 1 NOPRINT;  
BY TRT01PN _IMPUTATION_;  
MONOTONE LOGISTIC;  
VAR BASEBMI _3 _4 _5 _6 _7 _8;  
RUN;
```

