The imputation of missing post-baseline BSA, PSSI final score, NAPSI, and NRS scores will be performed using a similar method as described for PASI. The imputation of missing post-baseline PP PGA scores will be performed using a similar method as described for IGA. A pre-specified seed number of 132138 will be used in all imputation procedures. No imputation will be done to the health-related quality of life endpoints or safety endpoints.

- **Observed cases (OC)**: No imputation will be performed, only observed values will be analyzed.
- **m-NRI (response endpoint only)**: Subjects who used rescue medications or discontinued due to unsatisfactory therapeutic effect are considered as treatment failures (i.e., non-responder) for all time points after the initiation of rescue medications or subject discontinuation. For example, if a subject discontinued due to lack of efficacy, all visits

after the last planned visits will be imputed to non-responders. If a subject used rescue medication during the study, all visits after the start of the rescue medication will be imputed to non-responders regardless if the subject had an assessment or not. Other subjects with missing data will be kept as missing (i.e., no imputation). Discontinuation due to unsatisfactory therapeutic effect will be identified by discontinuation reason = "Other" with a comment "lack of efficacy" on the eCRF.

- **LOCF:** The last observed value will be carried forward for any subsequent missing values. Baseline values will not be carried forward.

A summary of the imputation methods for all efficacy endpoints is shown below:

Endpoint	Analysis Population	Imputation Methods
PASI-75 at Week 24	FAS	MI, m-NRI, LOCF, OC
	PP	m-NRI
IGA score of clear or almost clear at Week 24	FAS	MI, m-NRI, LOCF, OC
	PP	m-NRI
Change from Baseline and percent change from Baseline in PASI Total Score by Visit	FAS	MI, LOCF, OC
	PP	OC
PASI-50 and PASI-75 by Visit	FAS	MI, m-NRI, LOCF, OC
	PP	m-NRI
IGA score of clear or almost clear by Visit	FAS	MI, m-NRI, LOCF, OC
	PP	m-NRI
Change from Baseline and percent change from Baseline in BSA by Visit	FAS	MI, LOCF, OC
	PP	OC
Change from Baseline in NPSI by Visit	FAS	MI, LOCF, OC
	PP	OC
Change from Baseline in PSSI by Visit	FAS	MI, LOCF, OC
	PP	OC
Change from Baseline in PP PGA by Visit	FAS	MI, LOCF, OC
	PP	OC
Change from Baseline in NRS by Visit	FAS	MI, LOCF, OC
	PP	OC
Time to PASI-75	FAS	OC
Time to achieving an IGA score of clear or almost clear	FAS	OC
QIDS-SR 16	FAS	OC

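### A rescued subject is a treatment failure under Protocol 6.7, yet the primary multiple-imputation analysis of PASI-75 and IGA has no rule that stops such a subject counting as a Week 24 responder

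*SAP*

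**What the plan says.** Protocol Section 6.7, on rescue medication: "Subjects will be considered a treatment failure if rescue therapy is required; however, they can continue for safety monitoring, if required". The sentence is not limited to any population, endpoint or imputation method. Low-potency topical steroids on the face, axilla or genitalia, and medicated shampoos, are exempt: "This will not be considered as rescue medication".

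Protocol Section 8.7.3 makes MI the primary method for both co-primary endpoints, then adds: "MI will be implemented for all subjects with missing data, including those who used rescue medications and those who discontinued due to unsatisfactory therapeutic effect". The same section, just after placing rescued subjects and lack-of-efficacy dropouts in the per-protocol (PP) population, says: "These subjects will be considered as treatment failures (i.e., non-responder for both PASI-75 and IGA", for all time points after rescue starts or the subject discontinues.

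The SAP keeps this arrangement. Section 8 has "Subjects who used rescue medications or who discontinued due to unsatisfactory therapeutic effect will be included in the PP population", followed by the same failure definition. Section 9 repeats the MI sentence: "MI will be implemented for all subjects with missing data, included those who used rescue medications or discontinued due to unsatisfactory therapeutic effect". For the PASI models, "The imputations will include the following variables: baseline BMI, baseline PASI score, and PASI scores at the previous scheduled visits". Section 12.8.1 bases the primary analysis on the FAS with MI.

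Only the m-NRI item of SAP Section 9 carries an explicit override: once rescue has begun, "all visits after the start of the rescue medication will be imputed to non-responders regardless if the subject had an assessment or not". Under m-NRI, other missing data stay missing.

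**The concern.** Read on its own, Section 6.7 settles the matter: rescue means failure. The analysis that decides the trial does not apply it. After rescue, a subject may reach the response threshold on an observed score, or be given an imputed score that meets it. Either way the response goes to the randomised arm. For these subjects the primary response rate need not measure what Section 6.7 says it measures, and this affects both co-primary endpoints. Two programmers could also read the failure sentence in Protocol 8.7.3 and SAP 8 differently and produce different primary results.

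**Working it through.** **1. The plan's own figure.** SAP Section 7 assumes 15% response on placebo and 45% on PPC-06, with about 50 completers per arm. With a pooled null variance and two-sided 0.05: z = [0.30 − 1.96 × √(2 × 0.30 × 0.70/50)] / √[(0.15 × 0.85 + 0.45 × 0.55)/50] = 1.390, so power is 0.9177 per endpoint. Squared, treating the two endpoints as independent, this gives 0.842, matching the stated 84%. The calculation has no rescue input. The finding does not rest on it; it supplies only the two response rates used below.

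**2. Tracing a rescued subject through the primary analysis.**

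- Observed Week 24 score: SAP 11.4 keeps scores taken on drug or within 15 days of the last dose. It removes nothing because of rescue. The subject is classed on the score.
- Missing Week 24 score: SAP 9 imputes it. The stated models and example code, run separately by arm, use BMI and scores, with no rescue variable. Response is derived from the imputed score.
- Override: none under MI. LOCF and observed-case analyses have none either.

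| Analysis | Population and role | Rescue means non-response? | Other missing data |
|---|---|---|---|
| MI | FAS, primary | Not stated | Imputed |
| m-NRI | FAS sensitivity; PP supporting | Yes, explicit | Left missing |

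No planned analysis combines the failure rule with imputation for everyone else.

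**3. Illustrating size.** The documents give neither a rescue rate nor a response rate after rescue, so both are assumed. Let f be the share of an arm rescued and q the share of those credited as responders. Let p be response in everyone else, taken as 0.15 on placebo and 0.45 on active.

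- As written: p(1 − f) + f × q
- Failure rule: p(1 − f)
- Difference within an arm: f × q
- Odds ratio (OR) = [a/(1 − a)] / [b/(1 − b)], with a the active and b the placebo rate

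Placebo and active rates as written:

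- f = 2% in both arms, q = 20%: 0.15 × 0.98 + 0.02 × 0.20 = 0.151; 0.45 × 0.98 + 0.02 × 0.20 = 0.445
- f = 20% placebo and 10% active, q = 20%: 0.15 × 0.80 + 0.20 × 0.20 = 0.160; 0.45 × 0.90 + 0.10 × 0.20 = 0.425
- f = 10% placebo and 30% active, q = 30%: 0.15 × 0.90 + 0.10 × 0.30 = 0.165; 0.45 × 0.70 + 0.30 × 0.30 = 0.405

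| f placebo / active, q | As written | OR | Failure rule | OR |
|---|---|---|---|---|
| 2% / 2%, 20% | 15.1% vs 44.5% | 4.51 | 14.7% vs 44.1% | 4.58 |
| 20% / 10%, 20% | 16.0% vs 42.5% | 3.88 | 12.0% vs 40.5% | 4.99 |
| 10% / 30%, 30% | 16.5% vs 40.5% | 3.44 | 13.5% vs 31.5% | 2.95 |

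The risk difference moves by (f active − f placebo) × q when q is equal: 0, −2 and +6 points.

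**4. Does the choice of base matter?** The 15% and 45% could instead be the rates with rescued subjects already counted as failures. The failure-rule OR is then (0.45/0.55)/(0.15/0.85) = 4.64, and the as-written rate is p + f × q. The three cases become 15.4% vs 45.4% (OR 4.57), 19.0% vs 47.0% (OR 3.78) and 18.0% vs 54.0% (OR 5.35). The levels change; the direction in each case does not. Effects on the imputation models are not included in any figure.

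**The case against.** **MI was a deliberate choice.** Protocol 8.7.3 and SAP 9 name rescued subjects and apply MI to them. The failure rule follows the mention of the sensitivity analyses and is set out in full under m-NRI. This can be read as one scheme: MI primary, failure rule in sensitivity and supporting analyses. Protocol 8.10 says the SAP prevails. Much of this stands. But 8.10 only decides which text governs; it does not align Section 6.7 with 8.7.3. SAP Section 13 lists only the palmoplantar (PP PGA) change and declares no departure from 6.7.

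**The failure sentence already covers the FAS.** In both documents it directly follows inclusion in the PP population. If it is read as general, Protocol 8.7.3 contradicts itself, because the MI sentence then names the same subjects as imputed.

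**Section 6.7 is thin support.** It sits under concomitant therapy and names no endpoint. That is fair, but 8.7.3 and SAP 8 supply the definition: non-response on both.

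**Exposure may be small.** Most active psoriasis treatments are prohibited, low-potency steroids and medicated shampoos are exempt, and scores more than 15 days after the last dose are dropped. This stands. The documents support no lower limit on rescue use, and at 2% the effect is negligible.

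**m-NRI already reports it.** A failure-rule result on the FAS is planned for both endpoints, so it would be wrong to infer that the rule is never analysed. It does not stand in for the primary result, because it leaves all other missing data out in a trial that assumes 50% dropout.

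**Conclusion.** The concern holds as a conflict within the protocol, Section 6.7 against Section 8.7.3. The SAP repeats the MI rule of 8.7.3 without resolving it. As written, a rescued subject can be a Week 24 responder in the primary analysis of both co-primary endpoints.

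The textual gap is certain; its consequence is not. An arm's response rate is raised by about f × q, which is negligible if rescue is rare and several points if it is common. The odds ratios above are illustrations on assumed shares.

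Three stronger readings are tempting and unsupported:

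- That the primary analysis favours the drug. It does so only if active-arm subjects are rescued, or credited after rescue, sufficiently more often than placebo subjects. The documents say nothing on either.
- That it is usually conservative. Counting cases over a range of assumed shares would be arbitrary and is not a probability.
- That the SAP alone departs from the protocol. The SAP never restates 6.7; the inconsistency starts in the protocol.

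The point should be fixed, but it does not by itself invalidate the primary analysis.

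**What to change.** Before unblinding, reconcile Protocol 6.7 and 8.7.3 with SAP Sections 8 and 9, so that one stated rule covers rescued subjects in the primary FAS analysis. To carry Section 6.7 into that analysis, state in SAP Sections 9 and 12.8.1 that after MI, in every imputed dataset, PASI-75 and IGA response is set to No at all visits after the start of rescue. Use the Section 6.7 meaning of rescue, with its exemptions. Keep the present all-MI analysis as a sensitivity analysis, and record the change in SAP Section 13.

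The cost is some SAP wording and a few lines of code. No new data are needed: Listing 16.2.4.2 already carries the rescue flag and medication dates. The downside is slightly lower response rates in arms with rescue.

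Three further steps are optional and not part of the required fix:

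- Setting post-rescue scores to missing before the imputation models are fitted. No passage requires this, and it would change other subjects' imputed values.
- Extending the override to discontinuation for lack of efficacy, as m-NRI does.
- Adding a run that counts every missing Week 24 response as non-response.
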